1.	Patients who will be identified as low-risk patients based on the standardized screening questionnaire. Low-risk group patients are those patients with previous reaction not suggestive of anaphylaxis AND not requiring hospitalization for the reaction OR reaction considered non-immunologic (e.g. diarrhea, nausea, yeast vaginitis) OR exposure to penicillin-containing antibiotic after the date of reported reaction with no anaphylaxis and hospitalization AND no serious types of delayed reactions such as Steven-Johnson syndrome (SJS), toxic epidermal necrolysis (TEN), acute interstitial nephritis (AIN), drug-induced hepatitis or other documented organ injury, drug rash eosinophilia systemic symptoms (DRESS), hemolytic anemia, drug-induced cytopenia, and serum sickness. Patients who had delayed reaction (onset more than 24 hours) of isolated, non-progressive

symptoms (such as rash/hives alone) also belong to this group.

	Exclusion Criteria for screening
1.	Patients who cannot tolerate amoxicillin by enteral route.
2.	Patients with no parents or legal guardian available to give both written and verbal consent to the oral challenge testing
3.	Patients with no available parents or legal guardian during the conduct of oral amoxicillin challenge testing
4.	Patients currently on antihistamine or have received antihistamine in the previous 48 hours
5.	Patients who are critically ill or unable to complete challenge testing due to intercurrent illness
6 .	Patients who have been vomiting more than twice in the past 24 hours or are actively vomiting
7.	Patients with respiratory symptoms warranting oxygen therapy or pulmonary finding of wheezing or stridor
8.	Patients identified as having anaphylactic reaction to penicillin in the EMR through TheraDoc system.

	Exclusion Criteria for oral amoxicillin challenge testing
1.	Patients who will be identified as no-risk patients based on the standardized
	screening questionnaire. No-risk group patients are those patients who are
	historically labeled with penicillin allergy in the EMR based on family history
	alone OR those who have tolerated penicillin after a concerning incident without
	any reaction OR with penicillin allergy label but deny any history of reaction to
	any form of penicillin on screening questionnaire
2.	Patients who will be identified as high-risk patients based on the standardized
	screening questionnaire. High-risk group patients are those patients with penicillin

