	allergy label on EMR with previous reaction suggestive of anaphylaxis OR
	requiring hospitalization/epinephrine administration for the reaction OR reactions
	considered immunologic (angioedema, joint pains) OR involving serious types of
	reactions such as Steven-Johnson syndrome (SJS), toxic epidermal necrolysis
	(TEN), acute interstitial nephritis (AIN), drug-induced hepatitis or other
	documented organ injury, drug rash eosinophilia systemic symptoms (DRESS),
	hemolytic anemia, drug-induced cytopenia, and serum sickness. Patients who were
	previously diagnosed with penicillin allergy by an allergist also belong to the high-
	risk group.

Number of Research Participants

We will screen approximately 800 patients and enroll approximately 60 patients in our study based on the weekly census of Rainbow 3, 5 and 6 floors over a span of 6 months (September 22, 2021– March 31, 2022).

Recruitment Methods

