The research participants will be identified through the TheraDoc database system. TheraDoc database is a clinical surveillance system used to monitor antibiotic stewardship initiatives in healthcare systems. University Hospitals is one of the health care systems that employs the clinical surveillance services of TheraDoc. Patients admitted in Rainbow 3, 5 and 6 floors with penicillin allergy in the EMR will be identified through the TheraDoc system. Based on review of patient's allergy reaction in the EMR, the patient will be deemed potential research participant or not. If the EMR record shows that patient's penicillin allergy does not imply anaphylaxis or indicates an unclear non-anaphylactic reaction, the patient will be included in the patients to be screened through a standardized questionnaire (will be conducted with patient's parent/s or duly designated legal guardian). Screening questionnaire is an integral part in standard of practice allergy delabeling process. The patient/parent or legal guardian will be approached directly in the patient's room by the investigator where questionnaire will be completed. Only patients with parents/legal guardians who are physically present in the patient's hospital room will be screened. Based on assessment of patient's penicillin allergy status through the standardized questionnaire, patients will be identified as belonging to the no-risk, low-risk or high-risk groups. Only patients identified under low-risk group will be eligible to undergo oral amoxicillin challenge testing. Patients belonging to high-risk group will be given proper referral guidance to see allergy/immunology for further evaluation and management. Patients identified as no-risk group will immediately be delabeled in the EMR without oral amoxicillin challenge testing. All contact and communication with the patients and patient's parent/s or legal guardian will be in person.

Setting

The conduct of this research project will be done at Rainbow 3, 5 and 6 floors inside patient's hospital room. The oral amoxicillin challenge testing will also be done in the patient's hospital room.

Consent Process

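### A child with a past serious reaction (SJS, TEN, DRESS or similar) who later tolerated penicillin fits both the no-risk and the high-risk definition, and the no-risk limb lacks the guard that the low-risk definition has

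*Combined protocol and SAP*

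**What the plan says.** Risk groups are assigned from a standardized questionnaire. The definitions stand in the inclusion and exclusion criteria.

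- **No-risk** (Exclusion Criteria for oral amoxicillin challenge testing, item 1). Three limbs are joined by OR: a label based only on family history; "those who have tolerated penicillin after a concerning incident without" any reaction; or denial of any past reaction.
- **High-risk** (same list, item 2). Any one of these suffices: a reaction suggesting anaphylaxis; a hospital stay or epinephrine for it; a reaction judged immunologic, for example angioedema or joint pains; or serious "reactions such as Steven-Johnson syndrome (SJS), toxic epidermal necrolysis", with the list running on to AIN, hepatitis or other organ injury, DRESS, hemolytic anemia, cytopenia and serum sickness. Children "previously diagnosed with penicillin allergy by an allergist" are added.
- **Low-risk** (Inclusion Criteria for oral challenge test, item 1). This also has a limb for later exposure to a penicillin, followed by the condition that there were no serious delayed reactions, with the same kinds of diagnosis listed.

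Before the questionnaire, screening exclusion 8 removes "Patients identified as having anaphylactic reaction to penicillin in the EMR through TheraDoc system". Recruitment Methods says that if the record "does not imply anaphylaxis or indicates an unclear non-anaphylactic reaction, the patient will be included in the patients to be screened".

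The actions differ by group. Under Recruitment Methods, "Patients identified as no-risk group will immediately be delabeled in the EMR without oral amoxicillin challenge testing". Step 4 of Study Procedures Methods makes this automatic and adds a chart note and a letter for the primary care physician. Step 5 sends high-risk children not yet seen by an allergist for referral, with a chart note of its own.

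**The concern.** Two stated rules can apply to the same child and lead to opposite actions. This matters most for serious delayed reactions. Under the no-risk reading, a child with past SJS or DRESS loses the label on history alone. The chart then says that nothing in the history points to penicillin allergy, the physician letter carries that message, and no allergist looks at the case. Under the high-risk reading, the chart says that the reactions fit true allergy closely, and the child is referred unless an allergist has already seen them.

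Reported results are touched as well. The split into risk groups is specific objective 1. Delabeling, guidance to the primary care physician and referral are secondary endpoints 1 to 3. Two team members could score identical questionnaire answers differently and both be following the text.

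**Working it through.** The plan has no figure to reproduce here, so the check is a side-by-side reading. Take a child with documented SJS attributed to penicillin who later completed a penicillin course without any reaction.

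1. **Does the child reach the questionnaire?** Yes, if otherwise eligible. Screening exclusion 8 and the record review under Recruitment Methods remove only recorded anaphylaxis. SJS is not anaphylaxis.
2. **No-risk?** Yes. The later-tolerance limb is sufficient on its own, and its wording for the earlier event does not limit type or severity.
3. **High-risk?** Yes. SJS is named, and no phrase withdraws the child because of later tolerance.
4. **Low-risk?** Not if the serious-reaction condition is read as applying to the reported reaction, which is the natural reading. The protocol therefore places this guard beside re-exposure in the low-risk group, where the child would at least be challenged. It omits the guard in the no-risk group, where the label is removed with no test.
5. **Does any sentence rank the groups?** Step 3 sorts children into three groups without an order. Step 6 bars challenge for anyone with an exclusion criterion, but no-risk and high-risk are both challenge exclusions, so it cannot choose between them.
6. **What follows?** Under no-risk: automatic delabeling, a chart note of no compatible history (untrue for this child) and the physician letter. Under high-risk: no delabeling, by implication, because secondary endpoint 1 delabels only no-risk children and low-risk children who pass; and referral if no allergist has evaluated the child.

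Steps 2, 3, 5 and 6 run the same way for every other diagnosis on the serious list. They also hold for the remaining triggers: hospitalization or epinephrine, angioedema or joint pains, an allergist diagnosis, and anaphylaxis first disclosed on the questionnaire. For those, however, the overlap alone does not show which group should win.

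**Size.** The plan expects to screen about 800 children and enroll about 60. It gives no expected split by risk group and no frequency of serious reactions followed by tolerance, so no percentage can be derived. Each child scored the other way moves one unit between the no-risk and high-risk counts.

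**The case against.** The strongest reply is that the prose definitions are not the working instrument. Groups are assigned by the questionnaire, and Risks to Research Participants places the selection criteria there. The algorithm and questionnaire are Appendices A and B, which are not in the text available for review, and an algorithm is where a branching order would normally sit. This stands as a limit: one cannot say that the plan has no order, only that the definitions contain none and conflict as written.

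Second, the no-risk chart note could hardly be written for a child with SJS, which suggests that such children were never meant to be no-risk. It does lean that way. But it describes documentation and is not an assignment rule, and it sits badly with a limb that expressly admits a concerning earlier event. Training by an allergy attending and the treating attending's permission lower the risk, but neither states a tie-break.

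Third, a reader might infer that high-risk should come first for every trigger. The documents do not support that. A child who had angioedema or received epinephrine and has since taken penicillin without reaction may reasonably be delabeled, and the study exists to remove labels that are not needed. Tolerance-first may be intended there, and the choice is clinical.

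Fourth, one could list every combination of history features that meets both definitions and report a count. Such a count only restates that later tolerance plus any trigger produces the overlap. It says nothing about how many children are affected.

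**Conclusion.** The point holds for the serious reaction types listed under high-risk. Read literally, the no-risk later-tolerance limb allows automatic delabeling after SJS, TEN, DRESS or the like, with an inaccurate chart note and no allergist review. The protocol's own low-risk wording shows the guard that is missing. For the other high-risk triggers the overlap is real, but it calls for a decision by the investigators and is not evidence of a wrong rule.

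The effect is probably confined to few children. It does not reach the primary endpoint, which rests on challenged children, and it does not alter who is challenged, since neither group is. It would be wrong to infer that the ambiguity exposes anyone to amoxicillin within the study.

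The conclusion assumes that Appendices A and B do not already settle the order. If they do, the defect shrinks to definitions that disagree with the algorithm.

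**What to change.** Add to the no-risk later-tolerance limb: *and the reaction was not one of the serious types listed under high-risk*. These children are then scored high-risk.

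For anaphylaxis first disclosed on the questionnaire, hospitalization or epinephrine, angioedema or joint pains, and an allergist diagnosis, the allergist co-investigator should decide before enrollment which group prevails and write that into the definitions. The algorithm, the questionnaire key and the analysis should use the same order. If Appendix A or B already sets one, align the definitions to it.

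The cost is one clause and a matching line in the questionnaire key, with no added patients or procedures. The downside is that a very few children who have since tolerated penicillin keep the label, with referral for those not already seen by an allergist. The clause does not sort out the separate overlap between no-risk and low-risk for tolerant children with no high-risk feature; the same pass through the definitions could state that order too.

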This step is subdivided into two graded steps: administration of 10% of the standard dose followed by administration of 90% of the rest of the standard dose separated by 30 minutes time interval (see Appendix D).

Administration of 10% of standard dose:

A set of baseline vital signs will be obtained by a trained study team member before initiation of step-wise amoxicillin oral challenge allergy testing. If vital signs are normal and no apparent contraindication to perform the test is identified, the testing will be commenced.

Patients will first receive 10% of the standard drug dose in the form of enteral amoxicillin (see Appendix D). A trained study team member will administer the oral amoxicillin dose and closely monitor and observe patients for 30 minutes at the bedside following dose administration for any sign or symptom of drug reaction.

At any point the patient will have any reaction to the initial 10% dose, testing needs to be stopped immediately. A trained study team member needs to assess the patient right away at bedside and should consider giving diphenhydramine by mouth (or by IV or IM as clinically applicable) if reaction does not meet criteria for anaphylaxis (see definition of terms – attached document). Diphenhydramine will be available at bedside prior to initiation of the oral amoxicillin challenge testing. Administration of diphenhydramine will be done by the study team member. The patient needs to be monitored for the next 2 hours postadministration of diphenhydramine for the progression of symptoms. The reaction needs to be documented in the patient's chart specifying the reaction observed and intervention given (see Appendix C.3).

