If the patient develops any symptom indicative of anaphylaxis (see definition of terms), epinephrine will be administered right away either by IV or IM (see Appendix D) and a rapid response alert or code will be called as indicated. Epinephrine will be available at bedside prior to initiation of oral challenge testing. Administration of epinephrine will be done by a trained study team member. Inhaled albuterol or supplemental oxygen will be administered if indicated. Administration of both will also be done by the study team member with the assistance of the patient's nurse. The event needs to be documented in the patient's chart specifying the reaction and the intervention given (see Appendix C.3). The patient will need to be monitored for progression of symptoms for the next 2 hours post-administration of epinephrine so a proper disposition can be made (remain on the floor or transfer to higher level of care)

Any patient who develops any type of reaction at any point during the administration of the initial 10 % dose will be labeled to have failed the test. This will also be documented in the patient's chart accordingly. The patient's penicillin allergy status will then be retained in the chart (see Appendix C.3). The patient will be provided proper guidance and recommendation to follow up with an allergist for further evaluation and management.

Administration of the remaining 90% of standard dose:

If the patient did not develop any reaction to the 10% initial oral dose of amoxicillin following 30 minutes of administration, another set of vital signs will then be obtained by a trained study team member. If vital signs are normal, then the patient can proceed to receive the remaining 90% of the test standard dose of amoxicillin (see Appendix D). A trained study team member needs to be present at bedside for 30 minutes following the administration of the rest of the 90% of the dose. Another set of vital signs will be obtained 30 and 60 minutes following the administration of the rest of the 90% of the dose.

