Costs to Research Participants

The cost of the delabeling procedure will be free to the patient/s. This would otherwise be a relatively expensive procedure if done in an allergist's clinic. The cost of the challenge medications (amoxicillin) will be billed to the patient/s insurance as these are medications used in standard of practice allergy delabeling process and as this study entails standard of practice delabeling procedure. If the patient/s will develop reaction to the challenge testing, the cost of the rescue medications will be part of the patient's standard of care cost and will be billed to the patient/s insurance as well.

Research Participant Compensation

There will be no compensation, in any form, given to research participants.

Provisions to Monitor the Data to Ensure the Safety of Research Participants

Data collection will take place at UH RBC premises. Data will be managed by the PI ([name]) and coinvestigators ([name], [name], [name], [name] and [name]) using REDCap database. REDCap (Research Electronic Data Capture) is a secure web application for building and managing online surveys and databases. Only the study PI ([name]) and study team members will have access to identifiable private information. The study team will monitor at least every 1- 2 weeks for accuracy and adherence to protocol.

Drugs and Devices

Amoxicillin – standard full dose is 45 mg/kg/dose (maximum total dose 1000 mg) – to be given only by enteral route (naso-gastric tube, oro-gastric tube, gastric-tube) in two graded doses: 10% initial dose and 90% dose.

Indication: "Challenge Dose Amoxicillin" in order

Diphenhydramine - 1 mg/kg PO or IV (maximum dose 50 mg) – 12.5 mg/5 ml formulation and 50 mg/vial preparation

Albuterol – 2.5 mg/3ml nebule

Oxygen – to be given by nasal cannula to maintain oxygen saturation more than 92 %

Normal saline (0.9 % NaCL IV solution) - 20 ml/kg as bolus as needed for hypotension

Epinephrine 1:1000 for rescue medication:

<50 kg: Epinephrine (1mg/mL) at 0.01 mg/kg/dose – will be given as Epinephrine Jr 0.15 mg/0.3 ml auto-injector

>50 kg: Epinephrine (1mg/mL) at 0.5 mg/dose – will be given as Epinephrine 0.3 mg/0.3 ml autoinjector

Additional Information

Please see attached protocol algorithm (Appendix A), screening questionnaire (Appendix B) and clinical event notes (Appendix C).

References

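### The procedures allow epinephrine by IV or IM, but the drug list provides only auto-injectors, assigns nothing to the IV route, and gives one product's concentration inconsistently.

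*Combined protocol and SAP*

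**What the plan says.** Study Procedures Methods, step 6, describes the challenge as a 10% dose followed by the remaining 90%. The instruction for anaphylaxis is the same under both doses: "epinephrine will be administered right away either by IV or IM (see Appendix D". The task is assigned to the study team: "Administration of epinephrine will be done by a trained study team member".

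Drugs and Devices gives the products under the heading "Epinephrine 1:1000 for rescue medication". The entry below 50 kg reads "Epinephrine (1mg/mL) at 0.01 mg/kg/dose – will be given as Epinephrine Jr 0.15 mg/0.3 ml auto-injector". The entry above 50 kg reads "Epinephrine (1mg/mL) at 0.5 mg/dose – will be given as Epinephrine 0.3 mg/0.3 ml autoinjector". Neither entry names a route.

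For a reaction short of anaphylaxis after the 10% dose, step 6 says the team member "should consider giving diphenhydramine by mouth (or by IV or IM as clinically applicable". The matching entry in Drugs and Devices is "1 mg/kg PO or IV (maximum dose 50 mg", with an oral formulation and a 50 mg vial.

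Step 6 also refers to Appendix D for the rescue medications in general. That appendix is not in the text available for this review, and the Additional Information section names only Appendices A, B and C as attached.

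**The concern.** The procedures authorise two routes for epinephrine. The product list supplies a means of delivery that fits one of them, taking an auto-injector not to be a device for IV use (general knowledge; the protocol does not say so). The participants are inpatients and may include children admitted for antibiotic therapy, so some will plausibly have a line in place and the IV option is a practical one.

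Study team members give the drug, some of them still in residency, and they are told to act at once. If route, product and concentration do not agree on paper, one possible result is delay. Another is that a listed concentration and dose are used by a route to which the text does not assign them. The event is expected to be rare, but it is the most serious one the protocol foresees.

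**Working it through.** The first check sets the sections side by side. The second is simple arithmetic on the listed products.

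**Routes against listed products**

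| Drug | Routes in step 6 | Drugs and Devices | Allowed route with no entry in the available text |
|---|---|---|---|
| Epinephrine | IV, IM (both dosing steps) | two auto-injectors, no route named | IV: no preparation, concentration or dose assigned to it |
| Diphenhydramine | mouth, IV, IM (10% step) | PO, IV; oral formulation and vial | IM: label only |

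For epinephrine, two routes are allowed, two auto-injector entries are listed, and none is for IV use. The same section does mark IV use for other items: diphenhydramine names IV and has a vial, and saline is described as an IV solution given as a bolus. The epinephrine entries have nothing comparable.

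**Concentration, from the protocol's own figures** (concentration = mg ÷ ml)

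- Stated: 1:1000, written as 1 mg/mL in both weight bands.
- Above 50 kg: 0.3 mg ÷ 0.3 ml = 1.0 mg/mL. This reproduces the stated figure.
- Below 50 kg: 0.15 mg ÷ 0.3 ml = 0.5 mg/mL, that is 1:2000. This does not match. At the stated 1 mg/mL, 0.3 ml would contain 0.3 × 1 = 0.3 mg, twice the 0.15 mg on the product.

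So the two listed products have two different concentrations under one heading.

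**Exposure**

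- Planned enrolment is about 60. If all were challenged, the instruction would cover up to about 60 children.
- The protocol gives no anaphylaxis rate; the section on risks says only that it is very rare. Over an assumed range of 0 to 2%, the expected number is 0 to 60 × 0.02 = 1.2, so about none or one child.

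**Supervision when the instruction would be used**

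The fellow is to be present for 30 minutes after each dose, and the doses are 30 minutes apart. Presence is therefore required to about 30 + 30 = 60 minutes. The result is read at 120 minutes. For roughly the last 120 − 60 = 60 minutes the fellow need only be 3 to 5 minutes away.

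**The case against.** The strongest objection is Appendix D. The route sentence itself sends the reader there, and so does the line on rescue medications. Appendix D may set out an IV preparation with its concentration and dose. This stands, and it limits the point to what the available text shows. A reader might infer that the protocol has no IV product or dose anywhere; the documents do not support that. A reader might also infer that an IV entry in Appendix D would contradict Drugs and Devices. That does not follow either, because the list does not claim to be complete and its epinephrine entries name no route. Such an entry could simply supplement it.

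Two further inferences go too far. The protocol does not call IV and IM interchangeable or say that they share a dose; it names both and points to Appendix D. Nor does it list a single 1:1000 auto-injector; it lists two products, and by arithmetic only one is 1:1000.

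The bedside is also better supported than the wording alone suggests. The team is trained by a pediatric allergy attending, a medical provider must be on the floor, residents are directly supervised for 30 minutes after each dose, and a rapid response or code is called when indicated. These measures lower the risk, but they do not make the two sections agree.

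Finally, diphenhydramine is a lesser matter. The list gives a dose, names IV and includes a vial. Only the IM label is missing, and the procedure leaves the route to clinical judgment.

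**Conclusion.** The point holds as an internal inconsistency in a rescue instruction. The procedures allow epinephrine by IV or IM. The only specification available supplies both weight bands as auto-injectors and assigns no preparation, concentration or dose to the IV route. Separately, the product below 50 kg is 0.5 mg/mL on the protocol's own figures, against a stated 1 mg/mL. The missing IM label for diphenhydramine is minor.

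The first conclusion is confined to the text available, because the content of Appendix D cannot be judged. The concentration mismatch does not depend on Appendix D, since both figures stand in the same entry.

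The instruction applies to every challenged child. It would be used in about none or one of them under the assumed 0 to 2% rate. The matter is one of operation and safety, and no endpoint, sample size or analysis changes. It should be settled before the first challenge because the consequence could be serious and the correction is cheap.

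The entries also show differences between written dose and device content. That is a separate question, and resolving it would not by itself settle the IV route.

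**What to change.** The investigators and pharmacy should reconcile step 6 of Study Procedures Methods (the 10% and 90% dosing sections), Drugs and Devices, and Appendix D. For each rescue drug, the permitted routes should agree with the listed products, concentrations and doses. The reconciliation should include the stated concentration of the epinephrine product below 50 kg and the IM route for diphenhydramine. The same reconciled table should then be used in the bedside order set, so that protocol and orders cannot diverge.

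Which routes, products and doses appear in that table is for the investigators and pharmacy to decide; this review proposes none.

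The cost is protocol wording and one check of the order set. No extra patients, visits or staff are needed.
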